
Inclusion criteria
	
 • Male or female patients ≥18 years of age. For Japan only: written consent is necessary both from the patient and his/her legal representative if he/she is under the age of 20 years. • Histologically documented advanced or metastatic solid tumors or lymphomas • Part 1: histologically confirmed renal cell carcinoma (RCC), pancreatic cancer, urothelial cancer, head and neck squamous cell carcinoma (HNSCC), diffuse large B-cell lymphoma (DLBCL), microsatellite stable colorectal cancer (MSS CRC), triple negative breast cancer (TNBC), cutaneous melanoma or mCRPC 
 • Patients with colorectal cancer must have microsatellite stable (MSS) disease as detected by PCR-based assay or mismatch repair proficient as detected by immunohistochemistry and confirmed RAS status (KRAS and NRAS) by standard testing of tumor specimen based on local available laboratory data. • Patients with unresectable or metastatic cutaneous melanoma must have confirmed BRAF V600E status by standard testing of tumor specimen, based on local available laboratory data. • Part 2: histologically confirmed diagnosis of advanced/metastatic NSCLC. For those with mixed histology, there must be a predominant histology 
 • Patients should have confirmed EGFR and ALK status when clinically indicated and performed per standard testing of tumor specimen based on local available laboratory data. • Part 3: histologically confirmed diagnosis of selected advanced/metastatic malignancies. Based on emerging data from Part 1, Part 2 and latest scientific literature along with discussion between Novartis and study investigators, one or two tumor groups will be further explored in Part 3. As of protocol amendment 6, Part 3 will be opened to further assess TNBC patients with a PD-L1 SP-142 IC score of 0 (<1%). A second tumor group will be considered for Part 3 after completion of Part 1. • Safety run-in part in Japanese patients can enroll any tumor type included in Parts 1, 2, and 3. • Patient (except for those participating in Japanese safety run-in) must have a site of disease amenable to biopsy, and be a candidate for tumor biopsy according to the treating institution's guidelines. Patient must be willing to undergo a new tumor biopsy at screening, and again during therapy on this study. The use of recent sample is permitted under the following conditions (both must be met):

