5.1 Patient population

Adult patients (≥ 18 years) with advanced or metastatic solid tumors or Diffuse Large B-cell lymphomas will be enrolled in the study.

Patients enrolled in this study are not permitted to participate in additional parallel investigational drug or device studies. Patients who have completed the study may not be re-enrolled for a second course of treatment. Patients who do not initially meet all of the inclusion

or exclusion criteria may be re-screened for consideration in the trial. If a patient is rescreened, the same patient ID number should be used.

The investigator or designee must ensure that only patients who meet all the following inclusion and none of the exclusion criteria are offered treatment in the study.

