5.2 Inclusion criteria

Patients eligible for inclusion in this study have to meet **all** of the following criteria:

1. Male or female patients ≥ 18 years of age.
For Japan only: written consent is necessary both from the patient and his/her legal representative if he/she is under the age of 20 years.
2. Histologically documented advanced or metastatic solid tumors or lymphomas
 - a. **Part 1:** histologically confirmed renal cell carcinoma (RCC), pancreatic cancer, urothelial cancer, head and neck squamous cell carcinoma (HNSCC), diffuse large B-cell lymphoma (DLBCL), microsatellite stable colorectal cancer (MSS CRC), triple negative breast cancer (TNBC), cutaneous melanoma or mCRPC
 - Patients with colorectal cancer must have microsatellite stable (MSS) disease as detected by PCR-based assay or loss of mismatch repair (MMR) protein expression by immunohistochemistry and confirmed RAS genotype by standard testing of tumor specimen based on local available laboratory data.
 - Patients with unresectable or metastatic cutaneous melanoma that have confirmed BRAF V600E status by standard testing of tumor specimen by local available laboratory data.
 - b. **Part 2:** histologically confirmed diagnosis of advanced/metastatic NSCLC. For those with mixed histology, there must be a predominant histology
 - Patients should have confirmed EGFR and ALK genotype when clinically indicated and performed per standard testing of tumor specimen based on local laboratory data.
 - c. **Part 3:** histologically confirmed diagnosis of selected advanced/metastatic malignancies should Part 3 be opened to enrollment. As of protocol amendment 6, Part 3 will open and enroll TNBC patients with PD-L1 SP-142 IC=0. A second tumor group may be considered for Part 3 following analysis of data from Part 1.
 - d. **Safety run-in** part in Japanese patients can enroll any tumor type included in Parts 1, 2 and 3.
3. Patient (except for those participating in Japanese safety run-in) must have a site of disease amenable to biopsy, and be a candidate for tumor biopsy according to the treating institution's guidelines. Patient must be willing to undergo a new tumor biopsy at screening, and again during therapy on this study. The use of a recent sample is permitted under the following conditions (both must be met):
 - a. Biopsy was collected ≤ 6 months before 1st dose of study treatment
 - b. No immunotherapy was given to the patient since collection of biopsy.

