9.2 Site monitoring

Before study initiation, at a site initiation visit or at an investigator's meeting, Novartis personnel (or designated CRO) will review the protocol and CRFs with the investigators and their staff. During the study, the field monitor will visit the site regularly to check the completeness of patient records, the accuracy of entries on the CRFs, the adherence to the protocol to Good Clinical Practice, the progress of enrollment, and to ensure that study treatment is being stored, dispensed, and accounted for according to specifications. Key study personnel must be available to assist the field monitor during these visits.

The investigator must maintain source documents for each patient in the study, consisting of case and visit notes (hospital or clinic medical records) containing demographic and medical information, laboratory data, electrocardiograms, and the results of any other tests or assessments. All information recorded on CRFs must be traceable to source documents in the patient's file. The investigator must also keep the original signed informed consent form (a signed copy is given to the patient).

The investigator must give the monitor access to all relevant source documents to confirm their consistency with the CRF entries. Novartis monitoring standards require full verification for the presence of informed consent, adherence to the inclusion/exclusion criteria and documentation of SAEs. Additional checks of the consistency of the source data with the CRFs are performed according to the study-specific monitoring plan.

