[Table 14-18](#) shows 4 different scenarios for the interim analyses, where one or more groups having 10 or more patients treated. It has to be noted that the decision to stop or continue enrollment of patients in that group is made only if the number of patients in a group is at least 10. As stated in [Section 10.7](#) a group is stopped at interim if the probability of being “clinically meaningful” is less than 20%.

Scenario 1 considers the current available data, which is subject to change.

Based on the last interim analysis done, the decision was made to enroll 20 more patients to CRC RAS-wildtype (T9) at 160 mg NIR178 and CRC RAS-mutant (T10) at 160 mg NIR178. Decision was also made to stop enrolling RCC naive patients at 160 mg BID NIR178 (T5) and expand RCC naive patients at 240 mg BID NIR178 (T12) as a separate group. Final decision has also been made for TNBC (T6) group. Also, it was decided to stop further enrollment in Pancreatic (T2) and Urothelial (T4) groups. Hence, no further decisions will be made in the subsequent interim analyses for these groups, although the data will be included in the statistical model. Further decisions to stop enrollment or to expand will be made for groups DLBCL (T1), HNSCC naive (T3), Melanoma pre (T7), HNSCC pre (T8), RCC IO pretreated (T11), and mCRPC (T13).

For Scenario 2, none of the groups with at least 10 patients shows any activity (at interim, the relative posterior possibilities of “clinically meaningful” are less than 20%). In Scenario 3, for all groups that show some clinically meaningful activity with at least 10 patients treated, the proposed decision rule suggests to “continue” (posterior probability of “clinically meaningful” > 20%). The proposed statistical model shows reasonable decisions also under mixed scenarios 3 and 4.

Table 14-18 Hypothetical data scenarios and decision at interim

Scenario	Tumor Code	Tumor Type	No of responder/ No of patients	Observed ORR	Posterior probability of clinically meaningful response	Decision
1	T1	DLBCL	1/10	10%	0.1060	Stop
	T2	Pancreatic	0/14	0%	0.0175	Decided to stop
	T3	HNSCC naive	2/9	22.2%	0.2788	-
	T4	Urothelial	1/14	7.1%	0.0135	Decided to stop
	T5	RCC naive at 160 mg	4/11	36.4%	0.3167	Decided to expand*
	T6	TNBC	3/30	10%	0.2468	Final
	T7	Melanoma pre	0/2	0%	0.0850	-
	T8	HNSCC pre	0/3	0%	0.1970	-

Scenario	Tumor Code	Tumor Type	No of responder/ No of patients	Observed ORR	Posterior probability of clinically meaningful response	Decision

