2.2.6 Patient Classification

Patients may be excluded from the analysis populations defined above based on the protocol deviations (PD) entered in the database and/or on specific patient classification rules defined in [Table 2-2](#).

Table 2-2 Patient classification based on PDs and non-PD criteria

Analysis set	Protocol deviations leading to exclusion	Non protocol deviation leading to exclusion
Full analysis set	No written informed consent Mis-randomized patients as defined in Section 2.2.1	Patients who did not receive at least one dose of NIR178 or PDR001
Safety set	No written inform consent	Patient who did not receive at least one dose of NIR178 or PDR001 or did not have at least one valid post-baseline safety assessment.
PK Analysis Set	See definition of PK set	Patient who did not have at least one evaluable PK data for NIR178 or PDR001
IG Prevalence Set	No written informed consent	Patient did not have a non-missing baseline IG sample or at least one non-missing post-baseline IG sample
IG Incidence Set	No written informed consent	Patient did not have a non-missing baseline IG sample and at least one non-missing post-baseline IG sample
PK/ECG analysis set	See definition of PK/ECG set	Patient who did not have at least one post-dose matched PK-ECG record

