2.3.2 Demographics and other baseline characteristics

All demographic and baseline disease characteristics data will be summarized and listed. Categorical data (e.g., gender, age groups: 18- < 65, ≥65 years, race, ethnicity, ECOG performance status, smoking history, others as applicable) will be summarized by frequency counts and percentages; the number and percentage of patients with missing data will be provided. Continuous data (e.g., age, weight, height, body surface area, body mass index) will be summarized by descriptive statistics (N, mean, median, Q1, Q3, standard deviation, minimum and maximum).

BMI and BSA are calculated using the following formulas:

- $BMI [kg/m^2] = weight[kg] / (height[m]**2)$
- $BSA [m^2] = 234.94*(height[cm]**0.422)*(weight[kg]**0.515)/10000$

Diagnosis and extent of cancer

The summary and listing of diagnosis and extent of cancer (disease history) will include primary site of cancer, details of tumor histology/cytology, histologic grade, stage at initial diagnosis, time (in months) since initial diagnosis of primary site, time (in months) from initial diagnosis to first recurrence/progression, time (in months) since most recent relapse/progression, current extent of disease (metastatic sites).

Medical history

A listing of medical history and current medical conditions will be provided by primary system organ class (SOC) and preferred term (PT). Medical history and current medical conditions will be coded using the latest Medical Dictionary for Regulatory Activities (MedDRA) terminology available at the time of reporting.

Protocol deviations

The number (%) of patients with any protocol deviation will be tabulated by deviation category (as specified in the study Edit Check Specifications). All protocol deviations will be listed.

Analysis sets

The number (%) of patients in each analysis set (defined in [Section 2.2](#)) will be summarized and listed.

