2.5.2 Statistical hypothesis, model, and method of analysis

2.5.2.1 Part 1

This part will contain thirteen groups: (1) RCC IO naive at NIR178 160 mg BID, (2) RCC IO naive at NIR178 240 mg BID, (3) RCC IO pretreated at NIR178 240 mg BID, (4) pancreatic cancer at NIR178 160 mg BID, (5) urothelial cancer at NIR178 160 mg BID, (6) HNSCC IO naive at NIR178 160 mg BID, (7) HNSCC IO pretreated NIR178 160 mg BID, (8) MSS CRC RAS wildtype NIR178 160 mg BID, (9) MSS CRC RAS mutant NIR178 160 mg BID, (10) TNBC at NIR178 160 mg BID (11) melanoma IO pretreated NIR178 160 mg BID, (12) DLBCL at NIR178 160 mg BID, and (13) and mCPRC at NIR178 240 mg BID.

Note: The efficacy data from the Non-HNSCC patients, MSS CRC patients with unknown RAS status and melanoma IO naive patients will not be included in the statistical model. The efficacy data from any new treatment indications added to the existing 13 groups before the study closure (as a consequence of Protocol Amendment 5) that qualify the criteria for Part 1 may be used to inform the model.

All doses are given in combination with PDR001 400 mg Q4W. An adaptive Bayesian design ([Neuenschwander et al 2016](#)) will be used to assess activity of treatment in terms of overall

response rate (ORR) within each and across treatment indications. The design of the trial adapts to the data that are accumulated in the trial in such a way as to accommodate three possibilities:

- Scenario A: ORR is similar across treatment indications
- Scenario B: ORR is similar for some treatment indications and different in others
- Scenario C: The various treatment indications have distinct ORR

The pre-specified analysis is adaptive in the sense that when response is similar across all treatment indications (Scenario A), then it borrows information from across all the various treatment indications. In cases when few of the treatment indications have similar ORR (Scenario B), the model provides more precise estimates of ORR rates for the treatment indications that have similar response rates by allowing to borrow information only across these treatment indications. In the other possibility when the various treatment indications have distinct anti-tumor activity (Scenario C), the design allows little/no borrowing of information across treatment indications. In this case the trial will be similar to traditional stratified analysis.

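### Section 5.2 accepts loss of MMR protein by IHC as proof of MSS colorectal cancer, the reverse of the protocol summary: correct the line and confirm MMR/MSI status from existing records (minor)

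*Protocol*

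**What the plan says.** Protocol Section 5.2, criterion 2a (Part 1), requires that colorectal patients "must have microsatellite stable (MSS) disease as detected by PCR-based assay or loss of mismatch repair (MMR) protein expression by immunohistochemistry". The inclusion criteria in the protocol summary give the same PCR route but the opposite IHC result: "disease as detected by PCR-based assay or mismatch repair proficient as detected by immunohistochemistry". Criterion 4 of Section 5.2 and Table 10-1 both call the population MSS CRC.

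Section 5.1 makes the Section 5.2 list the operative one: "The investigator or designee must ensure that only patients who meet all the following inclusion and none of the exclusion criteria are offered treatment".

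Three safeguards are visible:
- Protocol Section 9.2 requires "full verification for the presence of informed consent, adherence to the inclusion/exclusion criteria".
- SAP Section 2.2.6 states: "Patients may be excluded from the analysis populations defined above based on the protocol deviations (PD) entered in the database". The full analysis set (FAS) row of Table 2-2 names only missing consent and mis-randomization as such deviations.
- SAP Section 2.3.2 states: "All protocol deviations will be listed".

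SAP Section 2.5.2.1 lists who is left out of the Part 1 model: non-HNSCC patients, plus "MSS CRC patients with unknown RAS status and melanoma IO naive patients will not be included in the statistical model". MMR status is not mentioned. A block after SAP Section 2.5.4 is redacted, and nothing is claimed about it.

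RAS wildtype (T9) and RAS mutant (T10) are judged on ORR with C1 = 5% and C2 = 13%. Protocol Section 10.7 gives them no separate interim analysis. The colorectal cohort was, however, expanded after an interim analysis and then split by RAS status (Protocol Sections 14.4.4 and 14.4.5; SAP Sections 1.1.1.1 and 2.8).

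**The concern.** Two current passages name opposite IHC results as evidence of the same status, and the reversed one sits in the list that investigators must apply. Read literally, it has two effects. An MMR-deficient patient could meet the criterion, and MMR-proficient IHC is not named as a qualifying route at all.

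A monitor who checks a chart against the written criterion could find it met, so the deviation-based safeguards might record nothing. At stake are the MSS label on T9 and T10 and the reading of their response rates. With thresholds of 5% and 13% in groups of under 30 patients, a few responders decide the result. The colorectal data also feed the borrowing model for the other groups.

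**Working it through.** **Inputs from the documents**
- Success rule (Protocol Section 10.4.2): posterior mean ORR at or above 0.13, and P(ORR ≤ 5%) below 0.10.
- Priors: Protocol Sections 14.4.1.1 to 14.4.1.3.
- Visible data: Table 14-18, scenario 1, with T9 0/11 and T10 1/19. Of this scenario Section 14.4.5 says: "Scenario 1 considers the current available data, which is subject to change".
- Illustrative final sizes: T9 n = 27 and T10 n = 28 (Table 14-19, scenario 4).

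**Inputs assumed.** The documents give neither a response rate for MMR-deficient patients nor a count of any admitted. Assumed: k = 2 deficient patients per group, response rate q = 30-50%, all other patients at 5%.

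**Step 1: reproduce the plan's figures.** As an approximation for Colon (MSS), use an exact two-stage binomial that stops at 0/10 and is positive at 4/30 or more.
- True ORR 5%: stop = 0.95^10 = 59.9% (Table 14-13: 59.8%); positive 5.1% (stated 5.8%).
- True ORR 20%: positive 81.4% (Table 14-14: 79.5%).
- With 1000 simulations, the standard error at 5.8% is √(0.058 × 0.942 / 1000) = 0.7 points, and at 79.5% it is √(0.795 × 0.205 / 1000) = 1.3 points.

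The full Part 1 mixture model was then rebuilt by grid integration. Table 14-19, scenario 4, posterior mean and P(ORR ≤ 5%):

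| Group | Rebuilt | Stated |
|---|---|---|
| T9, 4/27 | 0.1652, 0.0104 | 0.1653, 0.0118 |
| T10, 6/28 | 0.2015, 0.0005 | 0.2022, 0.0008 |

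**Step 2: cut-offs with the visible data as background.** All other groups are held at Table 14-18, scenario 1, and one colorectal group is varied.

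| Result | Posterior mean | P(ORR ≤ 5%) | Outcome |
|---|---|---|---|
| T9 3/27 | 0.112 | 0.091 | Fail |
| T9 4/27 | 0.141 | 0.027 | Success |
| T10 3/28 | 0.110 | 0.102 | Fail |
| T10 4/28 | 0.139 | 0.031 | Success |

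Four responders are needed in each group. The cut-off depends on the other groups: when they respond poorly, the rebuilt model needs 5/27.

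**Step 3: false-positive chance before any data.** P(X ≥ 4), with X = Bin(n−k, 0.05) + Bin(k, q).
- T9, k = 0: 1 − (0.2503 + 0.3557 + 0.2434 + 0.1068) = 4.4%.
- T9, k = 2: Bin(25, 0.05) + Bin(2, q) gives 10.2% at q = 0.3 and 16.1% at q = 0.5.
- T10, k = 0: 4.9%. With k = 2: 11-17%.
- Sensitivity to the count (T9): k = 1 gives 6.9-8.9%; k = 3 gives 14.5-26.3%.

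**Step 4: the same, given the visible data.** Both deficient patients are placed among those not yet shown.
- T9 has 27 − 11 = 16 patients to come and needs 4 more responders: 0.7% with k = 0, 2.8-5.4% with k = 2.
- T10 has 28 − 19 = 9 to come and needs 3 more: 0.8% with k = 0, 4.8-9.9% with k = 2.

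**The case against.** The strongest reply is that the controlling requirement is MSS disease. The IHC phrase may only name the test, meaning staining that looks for loss of MMR protein. Criterion 4, Table 10-1 and the summary all say MSS, and a site experienced in colorectal cancer would probably read it that way. Eligibility is fully verified, deviations are listed, and the study is closed out (SAP Section 4), so changing the line now alters no visible future enrolment.

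Most of this stands, and it is why the point is minor. It does not make the two passages agree. It also does not show what the verification would have recorded for a patient who met the criterion literally.

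Two further limits are accepted. The false-positive figures depend on a response rate and a count that the documents do not supply. And the sensitivity of a small group to one responder at its cut-off is close to true by definition, so it is not used as evidence here.

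A reader might infer that MMR-deficient patients were in fact enrolled, or that the colorectal cohort was never looked at before final analysis. The documents support neither. No enrolled patient's MMR status is reported, and the cohort was expanded after an interim analysis before the RAS split.

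**Conclusion.** Minor, and wrong as written: the operative eligibility line states the reverse of the intended IHC result. The contradiction rests on the text alone. Its consequence is only a possibility.

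If two deficient patients entered each group and responded at 30-50%, the false-positive chance before any data would rise by a factor of about two to four (4.4% to 10-16%; 4.9% to 11-17%). Given 0/11 and 1/19, it stays below 10% in both groups. These figures assume final sizes of 27 and 28, 5% response in all other patients, and the other groups as in Table 14-18, scenario 1.

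The visible total of 1/30 (3.3%) lies below C1, and the study closed for lack of sufficient efficacy. It would therefore go too far to infer that the trial's conclusion is in doubt. What remains open is whether the MSS label on T9 and T10 can be vouched for.

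**What to change.** 1. Reconcile criterion 2a with the summary, by amendment if one is still issued, otherwise by a documented clarification. Suggested wording: *MSS by PCR-based assay, or mismatch repair proficient (no loss of MMR protein expression) by immunohistochemistry.* An amendment needs the approvals in Protocol Section 12.1; a clarification costs one line.
2. Before final database lock, confirm the MMR/MSI method and result for the enrolled colorectal patients (58 by November 2019, per the Amendment 5 study status). Use existing eligibility and source records, take responders first, and check against the corrected wording. No new patients or procedures are needed.
3. Only if a patient proves to be MMR-deficient or MSI, list that patient and also report the Part 1 model without such patients in T9 and T10, keeping the FAS analysis primary. This costs one SAP paragraph, by amendment before lock or addendum after it (SAP Introduction), and one extra model run. If none is found, the SAP needs no change.
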